## **G Study Design**

### ***G1 Overview or Design Summary***

The study includes a Hybrid Type 2 (efficacy/implementation) cluster randomized trial. Since parent educators from each PAT site will be trained together (risk for contamination) and several research questions relate to the PAT site level, a cluster randomized trial is appropriate. PAT National Center will train educators affiliated with 40 PAT sites in HEALTH; among these, 20 will be randomly assigned to receive the HEALTH training curriculum (implementation strategy), and 20 will serve as controls, delivering usual care PAT. Given the multi-level nature of this study, there are two types of participants: 1) mothers and 2) PAT staff

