### **1.c Randomization Method**

PAT sites will be randomly assigned to HEALTH or usual care via a dynamic randomization scheme, in which percent of low-income and number of families served will be considered so that we achieve similar distributions in both arms of the study. The first 12 sites will be randomized to HEALTH or usual care arms in a 1:1 ratio within five site pairs where two sites are matched closely on total size and percent of low-income families. There are two sites that cannot be matched; for these two sites, several possible randomizations will be elicited in a 1:1 ratio and the randomization that best maintains the overall balance (on total size and percent of low income families) between the two treatment groups will be selected. Subsequent sites will use a dynamic randomization scheme, the details of which will be determined when those sites are recruited. Again, they will be randomized to best maintain the overall balance (on total size and percent of low-income families) between the two treatment groups.

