## **J Statistical Plan**

### ***J1 Sample Size Determination and Power***

We are confident the tabulated computations that led to our decision to randomize 40 sites (20 to each arm) are, if anything, conservative. Tabulations are based on weight at 24 months as the primary outcome and are for two-sided tests at the 0.05 significance level.

**Table 2:** Number of subjects required in each PAT site for two-sided tests at the 0.05 level of significance.

# PAT sites per group	Power	Between group difference	Intraclass correlation coefficient		
			0.01	0.02	0.05
19	0.8	4	6	6	7
	0.9	4	8	8	11

---

The table entries (Table 2, above) are the required sample size per cluster completing data collection for power values of .8 and .9; for ICC values of .01, .02, .and .05; for 19 PAT sites per group, and for between group differences of 4 between-group difference in the baseline to 24-month change in body weight that can be detected. Prior data from the HEALTH effectiveness trial found the standard deviation of the change in weight from baseline to 24 months was 8.3 kg. To be conservative, the computations assume an increased value of 10 for the standard deviation. The computations also assume 7 mother will complete 24 months of follow-up at each of 19 PAT sites. The number actually enrolled will be increased to 10 mothers (to account for a potential dropout rate of 30%) and 40 sites (20 per arm). Based on the above parameter assumptions, Table 3 indicates that to achieve a power of 0.8 with 19 PAT sites per group and an intraclass correlation coefficient as high as 0.05, the between-group difference in the change in weight from baseline to 24 months would have to be 4. Since the HEALTH study saw a 24-month decrease in weight of 1.5 (+/- 8.3) kg in the intervention group and a 24-month increase of 3.2 (+/-7.6) kg in the control, we are confident the target of 19 PAT sites per group with 7 mothers providing 24-month data is sufficient. We emphasize these computations are conservative because they allow for more variability (i.e., assume a larger standard deviation) than was observed in HEALTH, and because our analysis will add power by including data on the dropouts who do not provide 24-month data but who do provide data at 12 months.

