## ***J3 Statistical Methods***

Initial analyses will use t-tests and chi-square tests to compare baseline characteristics across groups. If continuous variables do not satisfy the normality or equal variance assumptions of the t-tests, we will explore data transformations and, if appropriate transformations cannot be identified, may employ Wilcoxon's test.

The primary analysis outcome, weight change between visits, was compared between intervention groups using a linear mixed-effect model with repeated measures. The model included a fixed effect for intervention group, time point, and the intervention

---

by time point interaction with a random effect for participants nested within site. In addition, we may employ models that adjust for covariates (e.g., income), if these are not balanced by randomization. The covariance structure will be determined after evaluating correlation coefficients across time and assessing both Akaike's Information Criterion and Bayesian information Criterion.

Secondary continuous outcomes will be analyzed with the same mixed-effect model. If model assumptions of normality are violated, data will be rank-transformed prior to analysis. The secondary binary outcome will be assessed using a binomial generalized estimating equation (GEE) model repeated measures, while secondary ordinal outcome (physical activity category) will be analyzed using a multinomial GEE model with repeated measures. Due to the multiple comparisons, only the primary endpoint—weight change from baseline to 24 months—will be reported as an unadjusted comparison. All other p-values will be adjusted for multiple comparisons using the Benjamini-Hochberg linear step-up procedure to control the false discovery rate across comparisons. Participants with missing data for all outcomes after baseline were excluded. Participants with at least one follow-up measurement (i.e., 12-month, 24-month, or both) were included in the analyses.

Mixed-effect analyses will also be conducted for subgroups. A per protocol analysis will also be conducted for participants completing at least four home visits. Least squares means with 95% confidence intervals will be report for changes from baseline. No adjustment for multiplicity will be applied to the confidence interval widths.

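### The random part of the primary model is worded so that it can be fitted with no between-site variance, although sites are the randomised unit

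*Combined protocol and SAP*

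**What the plan says.** Section 1.c makes the site the unit of randomisation: "PAT sites will be randomly assigned to HEALTH or usual care via a dynamic randomization scheme". Section G1 justifies this by the joint training of educators at a site and adds that, since "several research questions relate to the PAT site level, a cluster randomized trial is appropriate".

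Section J1 carries the clustering into the sample size. Table 2 gives the mothers needed per site "for ICC values of .01, .02, .and .05; for 19 PAT sites per group", and the tabulations "are for two-sided tests at the 0.05 significance level".

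Section J3 describes the primary analysis as a linear mixed model with fixed effects for arm, visit and the intervention "by time point interaction with a random effect for participants nested within site". The only other statement about covariance is: "The covariance structure will be determined after evaluating correlation coefficients across time and assessing both Akaike's Information Criterion and Bayesian information Criterion". The same mixed model serves the continuous secondary outcomes. The GEE models for the binary and ordinal outcomes are described by their repeated measures only.

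No section names a separate site effect, a site-by-visit effect, a variance robust to site clustering, or a degrees-of-freedom method.

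**The concern.** The random part is stated as one effect, its unit is the participant, and site appears only as the factor within which participants are nested. An analyst who codes that sentence as written would set the subject to participant within site. This gives each mother a unique identifier and models the correlation between her visits. Two mothers at the same site would be treated as independent. The covariance structure selected by information criteria concerns correlation over time, so it too works within a mother.

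In a site-randomised trial the arm contrast then has too small a standard error whenever the site ICC is above zero. At stake are the type I error and interval for the 24-month weight difference, which is the only comparison reported without multiplicity adjustment, and the same quantities for every continuous secondary outcome.

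**Working it through.** **Inputs, all from J1.** Difference 4 kg; SD of change 10 kg; 19 sites per arm and 7 completers per site for the power calculation; ICC 0.01, 0.02 and 0.05; two-sided 5% test; power 0.8 and 0.9; 10 mothers enrolled per site at 20 sites per arm, with 30% dropout. The true ICC is not given; these are planning values.

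**Step 1: does Table 2 include the site ICC?** Without clustering, the number per arm is n0 = 2 × [SD × (z for 0.975 + z for power) / difference]². With k sites per arm and design effect 1 + (m − 1) × ICC, the number per site is m = n0 × (1 − ICC) / (k − n0 × ICC).

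- Power 0.8: n0 = 2 × (10 × 2.802 / 4)² ≈ 98.1. For ICC 0.05, m = 98.1 × 0.95 / (19 − 4.9) ≈ 6.61. The three ICCs give 5.39, 5.64 and 6.61, rounded up to 6, 6, 7.
- Power 0.9: the three ICCs give 7.35, 7.86 and 10.04, rounded up to 8, 8, 11.

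All six cells of Table 2 reproduce, and 7 / (1 − 0.30) = 10 reproduces the enrolment per site. The design therefore counts on site variance entering the inference.

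**Step 2: what happens if the fitted model has no site variance?** The standard error is too small by a factor √DE, where DE = 1 + (m − 1) × ICC. The true two-sided size is 2 × [1 − Φ(1.96 / √DE)]. As a check, 20,000 null data sets per setting were analysed with a mother-level t-test, which ignores site.

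| Completers per site | ICC | DE | √DE | True size | 95% CI coverage | Simulated size |
|---|---|---|---|---|---|---|
| 7 | 0.01 | 1.06 | 1.030 | 5.7% | 94.3% | 5.6% |
| 7 | 0.02 | 1.12 | 1.058 | 6.4% | 93.6% | 6.5% |
| 7 | 0.05 | 1.30 | 1.140 | 8.6% | 91.4% | 8.7% |
| 10 (no dropout) | 0.05 | 1.45 | 1.204 | 10.4% | 89.6% | 10.6% |

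A t-test on site means in the same simulated data had a size between 5.0% and 5.1% in these four settings. At ICC 0 there is no inflation.

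**Step 3: the effect in kilograms, at 19 × 7 per arm and ICC 0.05.**

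- Site ignored: SE = 10 × √(2 / 133) = 1.226 kg; half-width 1.96 × 1.226 = 2.40 kg.
- Site included: SE = 10 × √(2 × 1.30 / 133) = 1.398 kg; half-width 2.74 kg (normal) or 2.84 kg (t with 36 df).
- Ratio: 1 − 1 / 1.140 = 0.12, so the interval that ignores site is about 12% too narrow.

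**Step 4: power with the site term in place.** For 4 kg at ICC 0.05 it is 81.6% (normal) or 79.5% (t with 36 df). It would be 90.4% if the ICC were ignored.

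**The case against.** The strongest reply is that the nested phrase is common shorthand for two levels: in many packages a site/participant formula expands into a site effect plus a participant-within-site effect. The context favours that reading. The authors chose a cluster design for stated reasons, randomised sites, and sized the trial with a site ICC. The repeated-measures covariance can already carry the within-mother correlation, so a random effect that mentions site is most naturally there for the clustering. The covariance sentence concerns another component and does not exclude a site term. No degrees-of-freedom method is named, so a wrong one has not been shown.

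All of this stands as an argument about intent, and it limits what can be claimed. A reader might infer that the primary analysis omits site variance and that its p-value and interval are therefore too optimistic. The documents do not support that: it is one of two readings, and nowhere do they say that site variance is left out. Nor should the 10.4% figure be taken as the expected size. It needs 10 completers per site, whereas J1 plans for 7, and an ICC of 0.05, which is the top of J1's range.

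What the reply does not do is settle the specification. A sample-size calculation does not bind the analysis model, and no other sentence supplies the site term. Two analysts could follow J3 faithfully and fit models with different error rates.

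**Conclusion.** J3 does not state that the primary model contains a between-site variance, and its literal reading contains none. This is more than a missing detail, because following the text as written can give a wrong primary p-value. Under that reading the true size is about 5.7% to 8.6% across the plan's ICCs with 7 completers per site, at most about 1.7 times nominal (8.6 / 5). At ICC 0.05 the interval is about 12% too narrow. With no dropout at all, 10.4% is the upper bound. If a site effect was always intended, the numerical consequence is nil and only the wording needs correcting.

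These figures assume the protocol's planning ICCs, equal site sizes and complete 24-month data in the mothers analysed.

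**What to change.** State in J3 that the primary model, and the same model for continuous secondary outcomes, has:

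- a random effect for PAT site, in addition to the correlation between a mother's visits;
- a site variance that may differ by visit (a site-by-visit term), or another device which ensures that the 24-month contrast carries the 24-month site variance;
- a test and interval for the 24-month arm contrast using small-sample degrees of freedom based on the number of sites, about 40 − 2 = 38. Kenward-Roger or between-within would both serve.

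The second item matters whichever response is used. If change at 12 and 24 months is modelled, a single site intercept forces the same site variance at both visits, and the 24-month standard error can still be too small if sites diverge over time. If weight is modelled with baseline as a visit, a site intercept shared by all visits cancels out of the change.

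Parts of J3 are in the past tense. If code already exists, the sponsor can check at once which model was fitted and report it.

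The cost is a sentence or two in J3, a small change in code and a slightly wider interval. The site term costs nothing against the stated power, since Table 2 already allows for the ICC. Using the t reference instead of the normal one takes power at ICC 0.05 with 19 sites per arm from 81.6% to 79.5%; the plan enrols 20 per arm. Whether the within-mother covariance should be fixed in advance is a separate matter and is not part of this point.

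### The GEE models for the secondary binary and ordinal outcomes specify no site-level clustering, although PAT sites are the randomised unit

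*Combined protocol and SAP*

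**What the plan says.** The unit of randomisation is clear. Section 1.c states that "PAT sites will be randomly assigned to HEALTH or usual care via a dynamic randomization scheme", and G1 explains why "a cluster randomized trial is appropriate". The sample size in J1 is built on a site-level intraclass correlation, "for ICC values of .01, .02, .and .05; for 19 PAT sites per group".

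J3 then describes three kinds of model:

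- **Primary weight outcome:** a repeated-measures mixed model with group, time and the group "by time point interaction with a random effect for participants nested within site". Site is named.
- **Continuous secondary outcomes:** the same mixed model, so site carries over.
- **Binary and ordinal secondary outcomes:** "The secondary binary outcome will be assessed using a binomial generalized estimating equation (GEE) model repeated measures", and the "secondary ordinal outcome (physical activity category) will be analyzed using a multinomial GEE model with repeated measures". No cluster unit, working correlation, variance estimator or small-sample rule is given here or elsewhere in the document.

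On multiplicity, J3 adds that "All other p-values will be adjusted for multiple comparisons using the Benjamini-Hochberg linear step-up procedure".

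**The concern.** A GEE has no random effect through which site could enter. Its allowance for dependence comes from the cluster that the analyst declares (and from any working correlation within it). The only dependence J3 mentions for these two models is repeated measures, that is, visits within a mother. An analyst who takes that literally makes the mother the cluster and so treats mothers at one PAT site as independent. The standard error of the arm comparison then omits between-site variation, and the p-values are too small.

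The Benjamini-Hochberg step does not repair this, because it takes the raw p-values as valid. The physical activity category bears on Hypothesis 1.2, so a pre-specified secondary hypothesis is exposed. Two competent analysts following J3 could also report different p-values from the same data.

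**Working it through.** **Inputs from J1.** Difference 4 kg, SD 10 kg, two-sided 0.05, ICC 0.01, 0.02 and 0.05, 7 completers per site, 19 sites per arm for the calculation and 20 per arm randomised.

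**Assumed.** The document gives no ICC for the binary or ordinal outcomes, so the range for weight is borrowed. The 18% event rate lies near the midpoint of the 11% and 26% with 5% weight loss in the earlier trial (F1). J3 does not name the binary outcome.

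**Step 1: reproduce the plan's own table.** With n0 = 2 × [10 × (1.96 + z_power)/4]², n0 = 98.1 at power 0.8 and 131.3 at 0.9. Inflating by 1 + (m − 1) × ICC and solving with 19 sites gives m = n0(1 − ICC)/(19 − n0 × ICC).

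- Power 0.8: m = 5.39, 5.64, 6.61, rounded up to 6, 6, 7.
- Power 0.9: m = 7.35, 7.86, 10.04, rounded up to 8, 8, 11.

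Every cell of Table 2 is matched, so the plan does size the trial for site clustering.

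**Step 2: effect of leaving site out, by design effect.** With DE = 1 + 6 × ICC, the true size of a nominal 0.05 test is 2 × [1 − Φ(1.96/√DE)].

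| ICC | DE | True size |
|---|---|---|
| 0.01 | 1.06 | 0.057 |
| 0.02 | 1.12 | 0.064 |
| 0.05 | 1.30 | 0.086 |

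**Step 3: simulation.** Null beta-binomial data, 20 sites per arm, 7 mothers per site, 18% event rate, log odds ratio at 24 months, independence working correlation, unrestricted allocation, 200,000 replicates per cell:

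| Analysis | ICC 0.01 | ICC 0.02 | ICC 0.05 |
|---|---|---|---|
| Cluster = mother, z | 0.055 | 0.062 | 0.082 |
| Cluster = site, plain sandwich, z | 0.061 | 0.061 | 0.061 |
| Cluster = site, × 40/39, z | 0.057 | 0.057 | 0.058 |
| Cluster = site, × 40/39, t on 38 df | 0.050 | 0.050 | 0.050 |

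With the mother as cluster, event rates from 11% to 26% give 0.050–0.055, 0.057–0.062 and 0.078–0.085. A three-category ordinal outcome (equal, or 50/30/20) gives 0.056–0.058, 0.065 and 0.086 with the mother as cluster. With the site as cluster, 40/39 and t on 38 df, it gives 0.049–0.053.

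**Step 4: balanced allocation.** Section 1.c says of later sites that "they will be randomized to best maintain the overall balance (on total size and percent of low-income families) between the two treatment groups". Suppose those factors explain a share s of the between-site variance and are perfectly balanced. The true design effect at ICC 0.05 is then 1.30 − 0.35s, while an unadjusted site-clustered variance still reflects 1.30. The third column is 2 × [1 − Φ(1.96/√DE)]. The fourth is the two-sided tail of t on 38 df beyond 2.024 × √(1.30/DE).

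| s (assumed) | True DE | Cluster = mother | Cluster = site, unadjusted, t on 38 df |
|---|---|---|---|
| 0 | 1.30 | 0.086 | 0.050 |
| 0.25 | 1.2125 | 0.075 | 0.043 |
| 0.50 | 1.125 | 0.065 | 0.036 |
| 0.75 | 1.0375 | 0.054 | 0.029 |

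Balancing reduces the excess from mother clustering. It also makes the site-clustered test conservative unless the balancing factors are in the model.

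**The case against.** The strongest reply is that J3 does not say site will be ignored. The phrase about repeated measures is also used for the primary model, which does include site, so it may describe the visits and not the independent unit. G1 and J1 show a team that planned for clustering, and a GEE clustered on site would cover the repeated visits and fit the wording. This stands in part. A reader might infer that the plan commits to a mother-level analysis, and the text does not prove that. It does leave these two models without the site term that the mixed models have.

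Second, naming the site is not enough. At ICC 0.01 the plain site-clustered z test (0.061) is worse than mother clustering (0.055), and at 0.02 the two are about equal (0.061 against 0.062). This stands, and it is why the small-sample correction and the t reference belong in the fix.

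Third, the material error sits at the top of an ICC range borrowed from weight, and balancing could shrink it. This also stands and limits the size of the claim. Perfect balance is an upper bound on that shrinkage.

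**Conclusion.** The gap is real and should be closed. As written, the two GEEs carry no site-level clustering in a trial that randomises sites. The literal mother-clustered analysis has a type I error of about 0.055, 0.062 and 0.082 at ICC 0.01, 0.02 and 0.05, given an 18% event rate, 7 mothers per site and unrestricted allocation. The excess is small at 0.01 and material mainly at 0.05.

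Two stronger inferences are not supported:

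- **That the weight result is compromised.** The primary model names site and continuous secondary outcomes inherit it. Its natural reading is a three-level model, so only clarification is needed there.
- **That small-sample degrees of freedom would be free for the primary analysis.** If they are also used for weight, power for 4 kg at ICC 0.05 and 7 completers per site changes. At 19 sites per arm, SE = √(2 × 100 × 1.30/133) = 1.398, and power is 0.816 by the normal formula but 0.795 with t on 36 df. At 20 sites per arm, SE = √(2 × 100 × 1.30/140) = 1.363, and the figures are 0.835 and 0.816 (t on 38 df).

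**What to change.** For both GEE models, state in J3:

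- the cluster is the PAT site, with mothers and their visits inside it;
- the working correlation is independence;
- the variance is a small-sample-corrected sandwich, for example multiplied by K/(K − 1) with K the number of sites (40/39 as planned);
- tests and intervals use a t reference with K − 2 degrees of freedom (38 with 40 sites);
- site size and percent low-income, the factors balanced at randomisation, are covariates, because without them the corrected test is conservative under balanced allocation.

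The 0.050 calibration was obtained without covariates and under unrestricted allocation. The covariate-adjusted version is worth a short simulation once the allocation scheme for later sites is fixed.

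As a clarification only, say that the mixed model has a random intercept for site plus a participant-within-site effect (or the within-mother covariance chosen by the planned criteria), and name the degrees-of-freedom rule, with the power figures above in view.

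The cost is SAP text and a line of model code, with no new data. Compared with mother clustering, intervals for these outcomes widen by √DE × 2.024/1.96 = 1.063, 1.093 and 1.178, or about 6%, 9% and 18% at ICC 0.01, 0.02 and 0.05.

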## ***J4 Qualitative Methods***

The digital recordings from interviews will be transcribed. Two researchers will analyze the transcripts. For the adaptation analysis, coding will be guided by the work of Wiltsey Stirman et al. using a combination of deductive and emergent coding. For all other analyses, after reviewing the research questions, team members will read five transcripts using the first draft of a codebook. Each coder will systematically review the data and organize each statement into categories that summarize the concept or meaning. Once these transcripts are coded, they will be discussed to ensure accuracy of the codebook and inter-coder consistency. The codebook will be edited as needed prior to coding the remaining transcripts. All transcripts will be analyzed by two coders in NVivo11. Themes from coded transcripts will be summarized and highlighted with exemplary quotes.

